depression, anxiety, suicide risk, and social connectedness. If during the interview, research staff suspects elder abuse or severe neglect, or identifies unsafe living conditions (lack of heat in the winter months), the SC will provide the subject with information about care management services and the option of the SC making a referral for case management (if consent to release the subject's name and contact information to case management services is provided). The SC will then review next steps, including PI review for eligibility, the process of random assignment, and follow-up assessments (if eligible).

- **Randomization:** A simple randomization will be used in consultation with the study biostatistician. If eligibility can be confirmed by study coordinator at the baseline interview, the study coordinator will randomize the subject at that time. If there are any eligibility concerns, the study coordinator will notify the subject that randomization will happen at a later time. The PI will review baseline assessment data collected by SC's weekly to determine eligibility. The SC who conducted the baseline interview will call the subject to explain which condition (group) he/she was randomly assigned to. The SC will also describe next steps for initiating the intervention, answer any questions the subject has, and schedule the next follow-up interview.
- **Intervention/Control:** Those in the volunteer condition will meet with Lifespan to initiate the program. As per Lifespan requirements, a background check will be completed. If a subject fails the background check, Lifespan will notify the study team. Lifespan will not disclose the reason(s) why the subject did not pass the background check. They will only indicate that the subject did not pass. The study team will contact the subject and inform him/her that he/she cannot participate in the study. If a subject passes the background check, the RSVP volunteer coordinator will match the subject with a social volunteer activity. Those in the life review condition will be contacted by a study team member to give them information regarding this condition.

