- **Follow-up assessments:** Subjects will be maintained in the study for 12 months. The initial intervention session (i.e., training) will begin within two weeks of randomization. Follow-up research assessments will be conducted for both conditions by email or mail at 3 and 9 months (or in-person if the subject does not have e-mail access and would prefer to complete them in-person) and in-person at 6 and 12 months. An assessment must be completed no later than two weeks after the target assessment date.

e) Assessment Measures & Administration Schedule:

The following tables specify the assessment measures we propose to use in the study:

Screening measures

Measure Name and Citation	Construct Measured	Description & Psychometric Data	Estimated Administration Time
Demographic characteristics	Not applicable	Age, gender.	1 minute
3-item UCLA Loneliness Short Form	Loneliness	A score of 6 or above has been shown to predict mortality. ^{18,29}	1 minute
6-Item Screener	Cognitive functioning	These 6 items ask questions measuring orientation and short-term memory.	1-2 minutes
National Institute on Alcohol Abuse and Alcoholism (NIAAA) single-item test	Alcohol misuse	This single item has greater than 90% sensitivity and specificity in the detection of alcohol use disorder.	1 minute Screening and 6 month visit
The CAGE Questionnaire ³⁰	Alcohol misuse	This 4 item questionnaire will be used as an exclusion screen. A	1 minute

		score of 2 or above is considered clinically significant.	Screening and 6 month visit
Self-Assessed Literacy Questions	Literacy	2 self-assessed questions regarding reading and writing abilities needed for the study	1 minute

Descriptive measures, and psychiatric/medical covariates

Measure Name and Citation	Construct Measured	Description & Psychometric Data	Estimated Administration Time
Demographic characteristics	Not applicable	Age, race/ethnicity, gender, sexual orientation, employment status (and history), income, education, living situation, marital status, PCP name, emergency contact, self-report endorsement of felony conviction.	3 – 5 minutes in-person interviews
Brief Grief Questionnaire ³¹	Grief	This brief self-report measure assesses social functioning impairment associated with bereavement.	1 minute in-person interviews if applicable

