
g) Analytic Procedures:

Power analysis is conducted to test treatment effects by the intent-to-treat (ITT) analysis for the primary hypothesis. We assume a conservative 20% attrition rate and a 0.3 within-subject correlation. A sample size of N = 300 (or N = 150 per treatment group) will allow us to detect a small effect size of 0.2 for loneliness, with 80% power based on a two-sided type I alpha = 0.05. The assumed within-subject correlation of 0.3 reflects the relatively long time lag between consecutive assessments. The proposed sample size also has 80% power to detect 32% mediation effects for loneliness, a continuous outcome. If full mediation is not achieved for any of the mediators considered, 32% mediation effects are sufficiently large to be of clinical importance for the outcomes of interest.

Descriptive statistics will be computed to summarize distributions of each outcome, with means and standard deviations for continuous outcomes and percent for categorical outcomes. Two-sample t tests (or the Mann-Whitney-Wilcoxon rank sum test) and Chi-squares will be used to examine balance of treatment randomization for continuous (if distributions are highlight skewed) and categorical variables. The primary hypotheses are concerned about the effectiveness of volunteering on reducing loneliness vs. control. Examination of mechanisms (mediation, Aim 2) as well as dose-response relationships (Aim 3) and moderators (Aim 3) of the intervention will also be examined. Aim 1 (and Aim 3 H4 on moderation) will be tested using longitudinal regression models, while the mediation hypothesis (Aim 2) will be examined by structural equation models, and dose-response relationships (Aim 3) by structural mean models.

The two most popular longitudinal models are the generalized linear mixed-effect models (GLMM) and the weighted generalized estimating equations (WGEE). Weighting is based on inverse probability of drop-out, extending standard GEE from valid inference only under missing completely at random to missing at random, similar to GLMMs. For inference about treatment effects, both models can be applied. However, parametric

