GLMM requires distribution assumptions, making inference sensitive to departures from assumed distributional models.⁵⁹⁻⁶¹ The semi-parametric WGEE requires no such assumption, thereby providing valid inference for a broader class of data distributions. We will use both models; if discrepancy arises between the two, we will report the results based on WGEE. Both models address missing data under the missing at random (MAR) mechanism.⁶²⁻⁶⁴ Biased estimates may still arise if missingness follows the non-ignorable non-response (NINR) mechanism. Although quite rare, and we do not anticipate such a missing data mechanism in this study, we will examine this issue by performing sensitivity analyses under some non-ignorable missing data models.^{59,65} Structural equation models (SEM) will be applied to test the mediation hypothesis involving the putative mediators of usefulness and social support.⁶⁶ Again, the popular maximum likelihood (ML), generalized least squares (GLS), and weighted least square (WLS) estimates are all biased under MAR, if parametric assumptions are not met by data in the study.^{67,68} We will also use recent distribution-free methods for more robust inference.⁶⁷ If results differ significantly between the maximum and distribution-free methods, only estimates from the latter will be reported. Common indices for assessing goodness-of-fit include likelihood ratio, Akaike (AIC) and Bayesian criteria. For SEM, popular goodness-of-fit measures include chi-square test, the comparative fit index (CFI), the index of Tucker and Lewis (TLI), and Root Mean Square Error of Approximation (RMSEA).^{66,69,70}

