The ITT analysis for Aim 1 provides intervention effects averaged over all subjects randomized to the intervention conditions. When intervention compliance (volunteering hours/satisfaction for subjects in the volunteering condition) demonstrates a dose-response relationship, as we hypothesize in Aim 3, complier average causal effects (CACE) are appropriate; thus we will use them to test Hypothesis 3. CACE is a compliment to ITT analyses and provides an answer to a different question than is answered by ITT analyses (i.e., the result of complying vs. being offered an intervention).⁷¹ CACE provides valid causal inference because it maintains randomization and includes all subjects in the analysis, as with ITT.⁷² CACE provides different intervention effects for individuals depending on their levels of compliance, which can be quite informative, especially when there is large variability in intervention compliance and strong dose-response relationships. The ITT and CACE estimates from a similar intervention study by Gruenewald, et al.⁷³ show that not only were the CACE effect sizes much larger than their ITT counterparts (small ITT vs. large CACE effect size), but the temporal trend also reversed; while the ITT effect sizes decreased, the CACE effect sizes increased from 4 months to 12 months post intervention, indicating substantial heterogeneity in intervention compliance and strong dose-response relationships. Since volunteering time is only required for the volunteering condition, standard statistical models cannot be used to perform CACE analysis. The CACE approach enables an estimate of the treatment effect at each level of "compliance" (i.e., amount of hours volunteered), without the need for a measure of compliance in the control group. In this way, we will be able to tell how well volunteering reduces loneliness at different "doses" of volunteering. The two most popular methods for addressing intervention compliance are the parametric principal stratification (PS) and the semi-parametric structural mean model (SMM).⁷⁴⁻⁷⁶ Unlike the PS, the SMM not only allows for continuous dose variables, but also requires no parametric model for data distribution such as normality, thereby yielding robust inference for a broader class of data distributions. We will use the latest SMM based on the structural functional response models (SFRM) for our CACE analysis, which not only allow for continuous, but also multiple dose variables.⁷⁴⁻⁷⁶ We are particularly interested in potential non-linear dose-response relationships so that we may determine optimal dose intervention whereby increased exposure (i.e., number of hours volunteered) becomes less worthwhile (in terms of reducing loneliness).

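### A background check made after randomization, described for the volunteering arm only, ends study participation for those who fail, which is not reconciled with 12-month follow-up and ITT

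*Combined protocol and SAP*

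**What the plan says.** Section III.d describes randomization first and then, under Intervention/Control, the start of each condition. For the volunteering arm it says: "Those in the volunteer condition will meet with Lifespan to initiate the program. As per Lifespan requirements, a background check will be completed". The agency tells the study team that a subject has failed but not why, and then: "The study team will contact the subject and inform him/her that he/she cannot participate in the study". For the life review arm, the same paragraph describes only a contact to explain the condition.

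Other sections point the other way:

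- III.d, Follow-up assessments: "Subjects will be maintained in the study for 12 months".
- III.a, Design: repeated assessments to 12 months are planned for every subject.
- IV.4, Informed Consent Procedures: assessments are requested whether or not treatment is completed.
- III.g, Analytic Procedures: "The ITT analysis for Aim 1 provides intervention effects averaged over all subjects randomized to the intervention conditions". The complier average causal effect (CACE) analysis is likewise said to include every subject.

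Before randomization, both arms face a felony exclusion that relies on self-report (II.d); the baseline measures in III.e list "self-report endorsement of felony conviction". The 2022 addendum does not mention failed checks.

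**The concern.** The check can only find what self-report missed. In the volunteering arm a person so found is told to leave the study, while an equivalent person in the life review arm stays and contributes outcomes. The arms are then no longer comparable as randomized. Because the agency does not disclose reasons, the team cannot describe those removed or identify their counterparts among controls.

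The timing makes this worse. The check belongs to starting the program, and "The initial intervention session (i.e., training) will begin within two weeks of randomization". Removal would therefore normally come before the 3-month assessment and leave baseline data only.

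Bias follows only if those removed differ in later loneliness beyond what the model explains. If they would have been lonelier, removing them flatters volunteering. The target effect is small (0.2 SD), so a modest one-sided loss could matter. For Aim 3, a subject with no study hours is an ordinary point on the dose scale if followed; the CACE comparison suffers only if the outcomes are missing.

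**Working it through.** **1. The plan's own figure.** Section III.g claims 80% power for an effect of 0.2 with 150 per arm and two-sided alpha 0.05. It states: "We assume a conservative 20% attrition rate and a 0.3 within-subject correlation". The number of assessments and the estimator behind the claim are not given. Taking four post-baseline assessments with equal correlation 0.3, the variance of their mean is (1 + 3 × 0.3)/4 = 0.475, or 0.475 − 0.3² = 0.385 after baseline adjustment.

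- With 120 per arm (150 less 20%), power is 61.3%, or 70.4% baseline-adjusted.
- With 150 per arm and baseline adjustment, ignoring attrition, it is 79.7%.

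The 80% is therefore not reproduced once attrition is applied. That is a separate matter. It affects only which standard error (SE) is used below.

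**2. Standard errors.**

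- Implied by the plan's claim: 0.2/(1.960 + 0.842) = 0.0714 SD.
- After attrition, mean of four assessments: √(2 × 0.475/120) = 0.089 SD.
- After attrition, baseline-adjusted: √(2 × 0.385/120) = 0.080 SD.

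**3. Bias.** Let p be the share of the volunteering arm removed and R the difference in mean loneliness between those removed and those retained, after whatever the model adjusts for. The full arm has mean (1 − p) × retained + p × removed. The analysis sees only the retained mean, so the bias has size p × R. Two-sided type I error is P(|Z + bias/SE| > 1.96). Both p and R are assumptions.

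| p (of 150) | R (SD) | Bias (SD) | Share of 0.2 | Type I error, SE 0.0714 | Type I error, SE 0.089 |
|---|---|---|---|---|---|
| 1% (1.5) | 0.5 / 1.0 | 0.005 / 0.010 | 2.5% / 5% | 0.051 / 0.052 | 0.050 / 0.051 |
| 2% (3) | 0.5 / 1.0 | 0.010 / 0.020 | 5% / 10% | 0.052 / 0.059 | 0.051 / 0.056 |
| 5% (7.5) | 0.5 / 1.0 | 0.025 / 0.050 | 12.5% / 25% | 0.064 / 0.108 | 0.059 / 0.087 |
| 10% (15) | 0.5 / 1.0 | 0.050 / 0.100 | 25% / 50% | 0.108 / 0.288 | 0.087 / 0.203 |

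**4. What missing-at-random (MAR) methods recover.** The Aim 1 model in III.g lists condition, time, their interaction, age and gender. Suppose baseline loneliness is used as well, and those removed differ by a raw amount D that is the same at baseline and follow-up. At correlation 0.3 the model predicts 0.3 × D of the later difference, so (1 − 0.3) × D = 0.7 × D remains. A simulation of 3 million subjects gave remaining fractions of 0.699 to 0.700. With D of 0.5 to 1.0 SD the bias is 70% of the table values:

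- 1-2% removed: 0.0035 to 0.014 SD
- 5% removed: 0.0175 to 0.035 SD
- 10% removed: 0.035 to 0.07 SD

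For the largest of these, 0.07/0.080 = 0.87 and type I error is about 0.14.

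**The case against.** The strongest reply has four parts.

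*The wording may be loose.* The sentence sits under Intervention/Control, and the study may be shorthand for the volunteering program. The 12-month statement could be a general rule to which this is an exception, and the consent language may not have in mind someone barred from starting. This is possible, but staff following the sentence would still tell a randomized subject that participation is over, so it needs the same correction on either reading.

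*The analysis set is already defined.* ITT over everyone randomized suggests that a removed subject stays in the set with missing outcomes. This is a fair reading, and the text does not say such subjects are dropped. It does not bring back the outcomes that were never collected.

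*Missing data are planned for.* The models work under MAR, and for non-ignorable missingness the plan says "we will examine this issue by performing sensitivity analyses under some non-ignorable missing data models". That is a partial answer. MAR methods leave 70% of a stable difference in the case worked above, and the sensitivity analyses name no scenario for this one-arm mechanism. The 20% attrition figure is a sample-size allowance and does not address a loss built into one arm.

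*The size is assumed.* This stands. After a self-reported felony exclusion, failures may be one to three people. Nothing in the documents supports a 10% rate or a 1.0 SD difference, and the SE of 0.0714 gives the larger type I errors. The date on which check results arrive is also not stated, so loss before month 3 is likely but not documented.

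**Conclusion.** The concern holds. The documents establish that the check follows allocation, is described for one arm only, and ends study participation for those who fail. Nothing reconciles this with follow-up of all subjects or with ITT. That conclusion needs no assumed number.

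The size cannot be fixed from the documents. At 1-2% removed it is close to negligible: at most 0.02 SD, with type I error at most 0.059. At 5-10% removed with residual differences of 0.5 to 1.0 SD it is 0.025 to 0.10 SD, or 12.5% to 50% of the target effect. These figures assume that all post-baseline outcomes of those removed are missing. The flaw should be fixed because it departs from a principle the plan itself adopts and the remedy is cheap; a large bias has not been shown.

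**What to change.** Reconcile the Intervention/Control paragraph of III.d with the follow-up paragraph of III.d, the ITT and CACE text in III.g, and IV.4. State that a subject who fails the check:

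- receives no volunteer placement but remains in the study as randomized;
- is invited to the 3-, 6-, 9- and 12-month assessments;
- is analysed in the volunteering arm for ITT;
- enters Aim 3 with zero study hours.

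Report the number of failures. Keep any subjects already removed in the ITT set, and add a named sensitivity analysis that varies their missing outcomes over a stated range.

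The cost is a change to the protocol and the staff script, plus four assessment payments per affected subject ($10 + $35 + $10 + $35 = $90), with some staff time and travel. The agency's placement requirement is unaffected.

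An alternative is to complete the check in both arms before randomization. That removes the asymmetry, but adds about 150 checks and ends randomization at the baseline visit.
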